#### 7.5. Baseline data collection

Baseline assessment will be completed in person. Baseline assessment will include:

Questionnaire (participant completed): Participants will complete a baseline questionnaire pack containing the patient reported outcome measures listed below.

- EQ-5D-5L
- Health, social care and broader resource use (resource use questionnaire tailored for the population)

#### eCRF (staff completed):

- Contact details and contact preferences
- Demographics (including age, sex at birth, ethnicity, date of birth, self-reported gender, postcode for index of multiple deprivation)
- NHS number (or equivalent)
- Anthropometrics (height & weight for BMI (patient reported measurements will be accepted))
- Current pain score (NRS; 0-10)
- Current and recent (last 3 days) analgesia (including NSAID)
- Current and recent antimicrobial therapy for this episode of cellulitis (including length and route of administration)
- Current use of intravenous "street" drugs
- Clinical comorbidities (including diabetes, peripheral vascular disease, chronic venous insufficiency and morbid obesity; defined as a BMI of 40 and above)
- Other risk factors for steroid adverse events (including recent or previous gastric ulcers and proton-pump-inhibitor usage)
- Routine baseline observations (to calculate Eron and NEWS2)
- Cellulitis details, including:
  - Cellulitis severity will be captured by the Eron classification
  - Cellulitis anatomical location
  - Timing of cellulitis onset

- $\circ$   $\;$  Other clinical details of cellulitis
- Clinical frailty scale

#### GP Practice contact details

GP Practice contact details will be collected/checked on the medical notes by the site in order to send out the GP letter, but will not be collected on the eCRF or returned to ExeCTU.

#### Minimum baseline data, pre-randomisation

Of the data listed above, a minimum baseline dataset must be collected prior to randomisation, this includes; inclusion and exclusion criteria, confirmation of eligibility, confirmation of consent, baseline pain score, mobile phone number and the minimisation criteria (diabetes status, severity of cellulitis and prior antimicrobial therapy for this current episode of cellulitis).

All other baseline data will ideally be collected before randomisation, but if not, immediately after randomisation and prior to giving the IMP.

#### 7.6. Randomisation

Once collection of the minimum baseline data is complete, participants will be randomised on a 1:1 basis to either dexamethasone or placebo.

Participants will be randomised into the trial by a delegated member of the site team using an online randomisation service.

#### **ONLINE ACCESS FOR 24-HOUR RANDOMISATION**

Further information on how to randomise can be found in the separate 'Randomisation' work instruction contained in the Investigator Site File.

In any case where technical issues prevent the site team from accessing the online randomisation service, ExeCTU staff will be available within office hours to randomise on behalf of a delegated member of the site team. No back-up will be available out of office hours. Details for this procedure will be outlined in the 'Randomisation' work instruction.

Allocation will be stratified by recruiting site and then participants allocated using a minimisation algorithm with random element, to aid balance between the two study groups on the following factors:

- 1. Prior antimicrobial therapy for this current episode of cellulitis (yes/no)
- 2. Diabetes status, defined by a known diagnosis of either type 1 or type 2 diabetes mellitus (yes/ no)
- 3. Severity of Cellulitis (Eron Class 1 vs all other classes)

Once the online randomisation process is complete, the system will indicate to the user a blinded pack ID which should be dispensed to the participant, it will not indicate whether the participant has been allocated to receive IMP or placebo.

The online randomisation system will automatically send an email to ExeCTU and the site team confirming the randomisation has taken place and the pack ID allocated. Site staff will note in the medical records that the patient has been enrolled into the trial. Site staff will then complete and send

the approved letter to the participant's GP (e.g. via post or secure email) informing the GP that their patient has entered the trial.

#### 7.7. Blinding

This trial will be double-blinded and therefore neither clinicians nor participants will know which treatment has been allocated. This will be achieved by the IMP manufacturer over-encapsulating, packaging, and labelling the IMP and placebo doses to look identical. The IMP/placebo packs will be labelled with blinded pack IDs and the randomisation system will automatically assign a pack ID to be dispensed to the participant after randomisation is complete. Only the senior (unblinded) statistician, the IMP manufacturer and the developers of the randomisation system will have access to the master list which will indicate which pack IDs relate to placebo packs and which relate to dexamethasone packs.

The trial statistician(s) undertaking analyses will be blinded until the primary statistical analysis of the primary outcome is complete. Where possible, the research teams at the trials centre and sites will remain blinded.

#### 7.7.0. Emergency Unblinding

A trial-specific procedure is in place for emergency unblinding although with both the short-term intervention period and low risk of serious adverse events it is anticipated that the need for unblinding will be minimal. Emergency unblinding will be available 24/7 via a dedicated and automated phoneline. Further details will be provided in a separate unblinding work instruction.

If the person requiring the unblinding is a member of the investigating team, then a formal request to the PI or other delegated member of the team will be made who will then call the phoneline to trigger the unblinding.

Although the safety of the trial participants must always take priority, maintenance of the blinding is crucial to the integrity of the trial. Unblinding is strongly discouraged and should only occur for medical or safety reasons. Investigators should only break the blind when information about the participant's trial treatment is clearly necessary and will alter the appropriate medical management of the participant.

An assessment to unblind should be made in consultation with the clinical and research teams wherever possible. The treating clinician has the ultimate decision and right to unblind the participant.

#### ACCESS FOR 24-HOUR UNBLINDING

Further information on how to unblind can be found in a separate 'Unblinding' work instruction in the Investigator Site File.

Each time an unblinding occurs, an email alert will be sent to ExeCTU and the site team, informing them that the unblinding has happened (this email will not reveal the allocation). A member of the site team should document the details of the unblinding and reasons for it on the 'Unblinding' eCRF, in the investigator site file and in the medical notes.

Following an emergency unblinding the participant should be treated according to the treating clinician's assessment.

Trial committees, where required within their charters, will also be notified of any unblinding.

#### 7.8. Trial assessments

The timing of trial assessments is shown in Table 3.

Assessment / event	Baseline (in person)	Early follow up (text message survey † )							Late follow up (telephone)	
event	Recruitment (time 0)	T1‡	T2 ‡	T3 ‡	T4 ‡	T5 ‡	T6‡	14 days (±2) ^	90 days (±7) ^	
Eligibility screen	Х									
Consent	Х									
Randomisation	Х									
Study drug dispensed*	Х									
Intervention compliance data	Х			Х						
Demographics	X									
Anthropometry	Х									
Contact details	X									
Contact preferences	Х									
Comorbidities	Х									
Cellulitis details	Х									
Risk factors for steroid adverse events	X									
Frailty score (Rockwood  )	Х									
Current pain (NRS, 0-10)	Х	Х	Х	Х	Х	Х	Х	X		
PGI-I			Х		Х		Х	Х		
EQ-5D-5L	Х						Х	Х	Х	
Analgesia usage	Х							Х		
Antibiotic usage	Х							Х		
Complications potentially related to								Х		
dexamethasone (Re)admission to hospital								X		

Assessment / event	Early follow up (text message survey † )						Late follow up (telephone)		
	Recruitment (time 0)	T1‡	T2‡	T3‡	T4‡	T5‡	T6‡	14 days (±2)^	90 days (±7)^
Unscheduled healthcare usage								X	
Health, social care, broader societal resource use	Х								Х
Recurrence of cellulitis									Х
Adverse event review								X	Х

\*The first dose of study drug will be given **after** baseline assessments and randomisation have been performed, the second dose will be taken ~24 hours later.

†SMS survey is default option with options for face-to-face for inpatients or telephone call for outpatients if unable to complete SMS survey.

‡ The first follow-up text message (T1) will be received at the first available follow-up timepoint (~8am or ~8pm) after randomisation, the subsequent 5 follow-up texts (T2-T6) will be received every 12 hours thereafter. ^The anchor point (Day 0) is the date of randomisation.

#### 7.9. Follow-up assessments

All participants will be followed-up to 90 days after randomisation. The timing and frequency of research assessments is shown in Table 3.

Follow-up assessment in this trial will occur remotely for participants discharged after initial assessment and recruitment (the majority, estimated to be 80% of all participants).

Remote assessment in the first three days post randomisation will be via text message surveys. All participants will receive a text message twice a day (at 8am and 8pm) asking them to complete a survey to collect key outcomes. A similar (text message based follow-up) approach is being utilised in the recently funded HTA trial in primary care cellulitis (COAT, NIHR134867). For participants unable to complete on a mobile phone, a telephone follow-up option may be offered depending on staff capacity. Participants admitted to hospital will be offered in-person visits by a member of the study team for data collection where possible or they can continue to provide pain scores remotely if preferred. This flexibility is to ensure the pragmatic running of the trial and encourage weekend recruitment/follow-up in sites which may not have research staff capacity at weekends.

At Day 14 (±2 days) post-randomisation, all participants will receive a phone call from a delegated member of the site team to record their analgesia usage over the first 3 days and antimicrobial usage up to the Day 14 call (as noted on participants' paper aide-memoire), current pain score (NRS), impression of improvement (PGI-I), unscheduled healthcare usage, health-related quality of life (EQ-5D-5L), adverse events, complications related to steroids and any hospital (re)admissions. Participants will receive a reminder text 2 days before their follow-up phone call is due; site teams will attempt to telephone them up to a maximum of 3 times.

At Day 90 ( $\pm$  7 days) post-randomisation, all participants will receive a further phone call to capture cellulitis recurrence, any adverse events, to complete the EQ-5D-5L and provide information regarding their health, social care and broader societal resource use to enable the cost-effectiveness analysis. Participants will receive a reminder text 7 days before their follow-up phone call is due; site teams will attempt to telephone them up to a maximum of 3 times.

Loss to follow-up is not expected to be high as the duration of follow-up and the intervention period are short.

#### 7.10. Withdrawal and change in participation status

Participants are free to discontinue from some or all aspects of the trial at any time if they wish to do so without having to give a reason and without detriment to their ongoing care. In addition, a participant may be withdrawn from any aspect of the study at the request of a healthcare professional if they feel it is within the best interest of the patient. In accordance with regulatory guidance, data that have already been collected will continue to be retained and used in the analysis.

Participants will be able to flexibly change their participation in the study by selectively ceasing any or all of the following aspects:

- Their allocated treatment
- Remote follow-up
- Passive data collection from medical records where relevant (except where required for reporting of serious adverse events)

Participants who withdraw consent for trial treatment prior to randomisation will be fully withdrawn from the study and no further data will be collected. These participants will not count towards the recruitment target.

A decision by a randomised participant that they no longer wish to continue receiving study treatment should not be considered a withdrawal of consent for follow-up or passive data collection from medical records unless the participant explicitly requests this.

PeRSEVERE principles will be followed for participants who cease to engage with the study (See: https://persevereprinciples.org/). If a participant becomes uncontactable and stops engaging with the study, passive data collection will continue where available from the medical notes (e.g. (re)admissions at Day 14) unless the participant expressly indicates they wish to withdraw. If a participant is not engaging with the study at a particular follow-up timepoint, attempts will still be made to contact them at the next timepoint unless they expressly indicate they wish to withdraw (e.g. if they don't answer their phone at the Day 14 timepoint, attempts should still be made to complete the Day 90 follow-up call).

If it becomes apparent that a participant has lost capacity and is unable to complete a follow-up timepoint (e.g. delirium at Day 14), this will be recorded in the eCRF but they will not be withdrawn from any aspect of the trial unless a personal consultee requests this. Their original consent will remain legally valid and unless withdrawn by a consultee they should be contacted again at the next follow-up timepoint and a new assessment of capacity carried out.

All participants who change their participation status, or cease engaging with the study, will still have the option to receive information about the trial, including newsletters and end of trial results unless they opt not to receive them. The details and reason for change in participation status will be recorded in the participant's 'Change in Participation' eCRF and medical notes.

#### 7.11. End of trial

The trial will end for a participant after their 90-day follow-up assessment. The end of the trial as a whole will be after the last 90 day follow up is complete, all data queries have been resolved, the database locked and the analyses completed. A declaration of end of study form will be submitted to the MHRA and NHS REC that awarded the favourable opinion within 90 days of the end of study.

If the study is terminated early, the study will end on the date the Sponsor formally declares the study terminated in writing. The MHRA and NHS REC will be notified of early termination within 15 days of the Sponsor deciding to end the study.

#### 8. TRIAL TREATMENTS

All participants will receive usual care for cellulitis including clinical assessment, antibiotics and analgesia in line with local policies, hospital admission if deemed required by the treating clinical team, together with advice on management of concomitant conditions (e.g. diabetes) and advice on expected symptom duration in line with NICE guidance (NG141).3

In addition to usual care, trial participants will be randomised on a 1:1 ratio to receive either:

• Dexamethasone 8mg orally on recruitment, then dexamethasone 8mg orally ~24 hours later.

#### OR

• Matched placebo capsules on recruitment, then matched placebo capsules ~24 hours later.

#### 8.1. Name and description of investigational medicinal product(s)

Dexamethasone (CAS 50-02-2) is the investigational medical product in this trial. Dexamethasone is a glucocorticoid (steroid) that is widely used for several indications. Glucocorticoids have a wide range of activities including modifying immune responses and altering body-wide homeostatic responses. Dexamethasone can be given orally, intravenously, intramuscularly or in a variety of topical forms. In this trial the oral form of dexamethasone is being used.

#### 8.1.0. Rationale for choice of dexamethasone as study drug and dose

Dexamethasone was chosen as a) it has the most glucocorticoid activity of all commonly used oral steroids and is therefore the most anti-inflammatory; and b) there is significant recent clinical experience of dexamethasone in both clinical trials and practice e.g. RECOVERY trial. As this trial has a patient reported primary outcome, placebo control should reduce bias. This trial therefore uses matched placebo for the control group.

The dose (8mg), route (oral), and course of dexamethasone chosen (2 doses) was based on expert opinion and published trial data suggesting additional benefit of a second dose at ~24 hours in a trial of dexamethasone with a primary outcome of pain . Given the half-life of dexamethasone, it is expected that the selected dose/course will continue to have an effect on swelling and pain over the next 24-48 hours.

#### 8.2. Regulatory status of the drug

Dexamethasone has marketing authorisation in the United Kingdom.

The IMP is being processed for this trial (for blinding purposes) in the following ways; deblistering and over encapsulation with backfill before repackaging into HDPE bottles, labelled as per MHRA annex 13 labelling requirements. Piramal Healthcare UK Limited will complete these activities, as subcontracted by the IMP supplier for this trial, MODEPHARMA Ltd.

#### 8.3. Product Characteristics

For details of product characteristics refer to the provided Summary of Product Characteristics (SmPC).

#### 8.4. Drug storage and supply

Full details can be found in the pharmacy manual. The dexamethasone and placebo will be provided directly to sites by the contracted IMP supplier. It will be delivered to sites in batches with the first delivery prior to site greenlighting. Deliveries will be receipted by the pharmacy department at sites and recorded as received on a study specific IMP management database. Stock of the study drug (and placebo) packs may be stored away from pharmacy (e.g. in an emergency department) if required and approved locally. This should be risk assessed at site level and appropriate storage conditions must be ensured as detailed in the pharmacy manual. Access should be limited to authorised members of the study team.

A drug accountability record will be maintained and updated by delegated site staff for all IMP packs provided and dispensed. The delegated persons at the sites will keep records of the receipt, dispensing, returns, quarantine or destruction of trial medication. The blinded pack IDs will be used to identify the packs on the accountability logs. A file note should be included in the Pharmacy Site File (PSF) directing to the location of these records. At the end of the trial, the drug accountability record should not be destroyed without Sponsor authorisation.

All data regarding the trial medication must be recorded either on forms provided by ExeCTU or on local accountability forms authorised by ExeCTU.

#### 8.5. Preparation and labelling of Investigational Medicinal Product

Preparation and labelling of the IMP will be completed by the contracted IMP supplier in accordance with Annex 13 of Good Manufacturing Practice (GMP) guidelines. Full details can be found in the pharmacy manual.

For blinding purposes, the active drug will be over-encapsulated. The participant will take two capsules per dose each capsule containing 1 x 4mg tablet of dexamethasone and backfill. Placebo capsules will be manufactured to match in appearance and will not contain any active ingredients. The capsules used may include bovine gelatin and are HALAL certified.

The active tablets have the following excipients; Maize starch, microcrystalline cellulose, lactose monohydrate, highly dispersed silicon dioxide, magnesium stearate. All capsules will contain a backfill made of one of these excipients.

Active and placebo capsules will be packaged into HDPE containers (4 capsules per container) with tamper-evident seals. All containers will be labelled with unique pack IDs.

#### 8.6. Dosage schedules

Participants will be administered one dose of 8mg of dexamethasone (2 x 4mg capsules) or matched placebo in hospital as soon as possible after randomisation. If the site team would prefer to delay the administration of the first dose for any reason, randomisation should be delayed where possible until a time where the first dose can be administered soon after randomisation.

If the participant is discharged before 24 hours from the first dose has passed, they will be given the second dose of 8mg dexamethasone or matched placebo to take home with clear instructions to take it ~24 hours after the first dose. Participants will be encouraged to take their second dose as close to the 24-hour timepoint as possible, within a window of 6 hours before to 6 hours after the 24-hour timepoint.

For participants that are hospitalised, they will be administered the first dose as usual, and the second dose prescribed on the drug chart (or electronic equivalent) for 24 hours later. The storage and management of the product between doses will be in line with the local NHS trust policies.

#### 8.7. Dosage modifications

No modification of trial dosage is permitted in the study.

#### 8.8. Known drug reactions and interaction with other therapies

A full list of known adverse effects of dexamethasone is detailed in the latest Summary of Product Characteristics (SmPC). Please see the risk section 2.4 for more information.

#### 8.9. Concomitant medication

Dexamethasone has some direct interactions with medications although the major reason it will be contraindicated is due to its known effects in patients with certain medical comorbidities, described fully in the risk section 2.4.

A list of medications that interact with dexamethasone are available at the British National Formulary (BNF) (https://bnf.nice.org.uk/interactions/dexamethasone/). Dexamethasone does not affect any kind of contraception.

The major concomitant medication that the BNF identifies as a potential interaction is NSAIDs, leading to a potential increased risk of gastric bleeding. The use of NSAIDs will be allowed when participating in this trial. Please see detail described in the risk section 2.4.

The SmPC for dexamethasone lists a precaution for use of live vaccines during treatment with dexamethasone due to the risk of viral infection. In line with national immunisation policies (the Green Book, Chapter 6), live vaccines should only be avoided when the duration of steroid is greater than one week. Therefore, no exclusion is necessary in this trial for those who have recently received a live vaccine, and live vaccines can be received as normal during participation in the trial, if deemed appropriate/necessary.

#### 8.10. Trial restrictions

Women of childbearing potential are required to use adequate contraception for the duration of their participation in the trial (3 months from randomisation), as defined in the eligibility criteria section 6. Breastfeeding mothers and pregnant people are not eligible to participate in this trial.

#### 8.11. Assessment of compliance with treatment

As only two doses of the drug are being taken 24 hours apart, adherence is expected to be high. Sites will record when the first dose is taken on the eCRF. Participants will be asked to confirm whether they have taken their second dose via their 3rd SMS survey (T3).

Term	Definition					
Adverse Event (AE)	Any untoward medical occurrence in a participant to whom a medicinal product has been administered, including occurrences which are not necessarily caused by or related to that product.					
Adverse Reaction (AR)	An untoward and unintended response in a participant to an investigational medicinal product which is related to any dose administered to that participant.					
	The phrase "response to an investigational medicinal product" means that a causal relationship between a trial medication and an AE is at least a reasonable possibility, i.e. the relationship cannot be ruled out.					
	All cases judged by either the reporting medically qualified professional or the Sponsor as having a reasonable suspected causal relationship to the trial medication qualify as adverse reactions. It is important to note that this is entirely separate to the known side effects listed in the SmPC. It is specifically a temporal relationship between taking the drug, the half-life, and the time of the event or any valid alternative aetiology that would explain the event.					
Serious Adverse	A serious adverse event is any untoward medical occurrence that:					
Event (SAE)	
 
Results in death.
 
Is life-threatening; an event in which the participant was at risk of death at the time of the event. This does not refer to an event which hypothetically might have caused death if it were more severe.
 
Requires inpatient hospitalisation or prolongation of existing hospitalisation.
 
Results in persistent or significant disability/incapacity.
 
Consists of a congenital anomaly or birth defect.
 
					
	Other 'important medical events' may also be considered serious if they jeopardise the participant or require an intervention to prevent one of the above consequences.					
	In this trial the following conditions will always be reported as serious adverse events:					
	
 
Gastrointestinal bleeds
 
Psychosis
 
Severe hyperglycaemia (defined for this trial as ketoacidosis, hyperglycaemic hyperosmolar state or hyperglycaemia requiring new use of insulin)
 
					
Serious Adverse Reaction (SAR)	An adverse event that is both serious and, in the opinion of the reporting Investigator, believed with reasonable probability to be due to the trial treatment, based on the information provided.					

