#### 2.4. Assessment and management of risk

Cellulitis is commonly treated in hospital emergency departments and other urgent care settings and is generally more severe than when patients present in primary care.

The intervention group for this trial will be prescribed 2 x 8mg doses of dexamethasone to be taken orally 24 hours apart (+/- 6 hours). The comparator group will take 2 x matched placebo doses. Each 8mg dose of dexamethasone will be made up of 2 x 4mg tablets over encapsulated into two capsules, for blinding purposes.

A detailed risk assessment has been carried out by the Sponsor and will be maintained and updated throughout the trial. This trial has been characterised as Type B (somewhat higher than the risk of standard medical care) as the IMP (dexamethasone) has marketing authorisation but the DEXACELL trial will use the IMP outside of these specifications.

Extensive experience of short-course steroids in infection have not identified major safety concerns and patients with contraindications to dexamethasone will not be eligible to participate in the trial. Dexamethasone is already indicated for several conditions, including short term local treatment of inflammation, suppression of inflammatory and allergic disorders, croup (a respiratory viral condition in infants), treatment of COVID-19 requiring supplemental oxygen, and a variety of other conditions. The dosage being used in this trial is much lower than dosages recommended for some conditions, e.g. in idiopathic thrombocytopenic purpura 40mg doses are recommended daily for up to 4 days and in some cases of acute cerebral oedema doses of up to 64mg per day are given for days to weeks. Comparing with other infectious diseases, in this trial a total dose of 16mg will be given; when compared to 400mg recommended in adjunctive therapy for meningitis this is a 25 fold difference.

Information about possible benefits and risks of participation will be described in the Participant Information Sheet (PIS).

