\* The first follow-up text message (T1) will be received at the first available follow-up timepoint (~8am or ~8pm) after randomisation, the subsequent 5 follow-up texts (T2-T6) will be sent every 12 hours thereafter.

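### Second-dose compliance is asked only at T3, while the permitted dose-2 window is still open for many participants, and no later question recovers the answer

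*Protocol*

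**What the plan says.** Section 8.11 has sites record when dose 1 is taken. For dose 2 it relies on self-report: "Participants will be asked to confirm whether they have taken their second dose via their" third SMS survey, T3. In Table 3 (section 7.8) the row "Intervention compliance data" is marked at baseline and T3 only. The Day 14 call described in section 7.9 has no dose-2 question, and neither does the Day 90 call.

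The survey clock is tied to randomisation. T1 "will be received at the first available follow-up timepoint (~8am or ~8pm) after randomisation", and "the subsequent 5 follow-up texts (T2-T6) will be sent every 12 hours thereafter" (footnote to Table 1).

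The dosing clock is tied to dose 1. Section 8.6 has dose 1 given "in hospital as soon as possible after randomisation" and accepts dose 2 "within a window of 6 hours before to 6 hours after the 24-hour timepoint"; section 2.4 gives the same rule, "24 hours apart (+/- 6 hours". Section 8.6 also states: "Participants will be encouraged to take their second dose as close to the 24-hour timepoint as possible".

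Compliance is to be reported descriptively by allocated group (section 10.2.2).

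**The concern.** The two clocks do not fit together. A participant who follows section 8.6 can still be inside the permitted window when T3 arrives, truthfully answer that dose 2 has not been taken, and take it on time afterwards. The protocol describes no route by which that answer is corrected. The same holds for someone who misses T3 but answers T4 to T6: the dose-2 information is lost although the participant is still responding.

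This matters because dose-2 uptake helps to interpret a small or null effect. Section 8.1.0 bases the two-dose course partly on trial data suggesting added benefit from a second dose at about 24 h. Section 8.11 expects high adherence, so even a modest artefact could be a large part of the non-adherence observed. Section 10.2.1 leaves secondary estimands to the SAP, and any adherence-based one would inherit the misclassification.

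**Working it through.** **Inputs from the protocol.** T1 is the next 8am or 8pm, so it comes U hours after randomisation with U between 0 and 12. T2 to T6 follow at 12 h steps. The dose-2 window is 18-30 h after dose 1.

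**Inputs assumed, because the protocol gives none.** The lag L from randomisation to dose 1 is 0-1 h. Randomisation clock time is either uniform over 24 h (U uniform on 0-12) or uniform over 09:00-17:00 (T1 at 20:00, so U uniform on 3-11). Dose-2 times are centred on 24 h after dose 1, either normal with SD 1, 2 or 3 h and limited to the window, or spread evenly over the window.

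**Timing of T3.** T3 = U + 24, that is 24-36 h after randomisation. The window closes at 30 + L.

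**Window still open when T3 is sent.** This requires 24 + U < 30 + L, that is U < 6 + L.
- Uniform clock time: (6 + L)/12, so 6/12 = 50% at L = 0 and 7/12 = 58% at L = 1 h.
- 09:00-17:00: (6 + L - 3)/8, so 3/8 = 38% at L = 0 and 4/8 = 50% at L = 1 h.

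**T3 sent before the 24 h point itself.** This requires U < L. Under uniform clock time it is L/12: 0% at L = 0 and 8% at L = 1 h. For 09:00-17:00 it is 0% for any lag up to 3 h, because U is at least 3.

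**Dose 2 taken within the window but after T3.** This requires L + e > U, where e is the deviation of dose 2 from the 24 h point. For e spread evenly over -6 to +6 h:
- Uniform clock time: (6 + L)²/(24 × 12), so 36/288 = 12.5% at L = 0 and 49/288 = 17.0% at L = 1 h.
- 09:00-17:00: (3 + L)²/(24 × 8), so 9/192 = 4.7% at L = 0 and 16/192 = 8.3% at L = 1 h.

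The normal cases come from a simulation with 2,000,000 draws:

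| Clock time | Lag | Window open at T3 | Late dose, SD 1 h | SD 2 h | SD 3 h | Even spread |
|---|---|---|---|---|---|---|
| Uniform | 0 | 50% | 3.3% | 6.7% | 9.8% | 12.5% |
| Uniform | 1 h | 58% | 9.0% | 11.6% | 14.5% | 17.0% |
| 09:00-17:00 | 0 | 38% | 0.0% | 0.7% | 2.8% | 4.7% |
| 09:00-17:00 | 1 h | 50% | 0.1% | 2.1% | 5.3% | 8.3% |

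The late-dose columns suppose that everyone takes dose 2 inside the window and answers T3 at once.

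**Sensitivity.**
- Replies 1-2 h after the text, with uniform clock time and lag 0-1 h, lower the open-window share to 33-50% and the late-dose share to 0.1-12.5%.
- A 2 h lag raises the open-window share to 67% (uniform) or 62% (09:00-17:00).
- Randomisation concentrated at 12:00-20:00 raises it to 75% (lag 0) or 88% (lag 1 h), with late doses at 5-19% and 14-26%.

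**Same check at T4.** T4 = U + 36, so it is sent at least 36 h after randomisation. The window closes at 30 + L, which is no later than 36 h for any lag up to 6 h. The open-window share is then 0%.

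**The case against.** The strongest reply is that an open window does no harm once the dose has been taken. Participants are asked to dose near 24 h, and T3 is the first survey sent at least 24 h after randomisation for everyone. This stands. A reader might infer from the open-window share that about half of the compliance records are wrong. The documents do not support that; the relevant figure is the smaller late-dose share.

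Three other strong readings also fail.
- That a truthful answer of not yet is coded as not taken: the protocol does not state this. The survey wording, response options and coding are not shown. It is the natural result of a single question, but it is an inference.
- That many are asked before dose 2 is due: this rests entirely on the assumed lag. It is 0% at zero lag, and section 8.6 asks for randomisation to be held back where dose 1 would be delayed.
- That the error reflects time of randomisation alone: it also depends on when the participant takes dose 2.

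There are partial safeguards too. Section 3.3.0 records actual response times, so a reply given inside the window can be flagged. Inpatients have dose 2 prescribed on the drug chart. But flagging does not show whether the dose was taken later. Section 8.11 does not say that the chart entry reaches the eCRF, and section 7.9 expects about 80% of participants to be discharged after initial assessment. Both arms follow the same blinded schedule, so nothing suggests a bias that differs between them.

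**Conclusion.** The point holds as a data-collection gap: sections 8.6 and 8.11 need to be reconciled on when the dose-2 question is asked. With a lag of 0-1 h, the share who may be counted as non-adherent although they dosed within the window is about 3-17% under uniform clock time and about 0-8% for 09:00-17:00 randomisation. These ranges rest on assumed lag, clock times and dose-time spread. Prompt replies are also assumed; slower ones lower the figures, while longer lags or afternoon-weighted recruitment raise them. That T3 falls 24-36 h after randomisation, and that no later question is scheduled, needs no assumption.

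A reader might infer a threat to the trial's main result. There is none: the primary analysis is intention-to-treat with a treatment policy strategy (section 10.2.1) and does not use compliance. What is at stake is the accuracy of the descriptive compliance report and of any adherence-based analysis that the SAP may define. It is worth correcting because correction is cheap and the missing answers cannot be recovered reliably once data collection is over.

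**What to change.** In section 8.11 and Table 3, keep the question at T3 and repeat it at T4 for anyone who answers no or does not reply at T3. Record the date and time at which dose 2 was taken. T4 is an existing survey that already carries the pain score and PGI-I, so no contact is added.

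The cost is one survey edit, the matching change to Table 3, and about 12 h longer recall for those asked again. Keeping the T3 question avoids that longer recall for everyone else. The change concerns only when the question is asked; the dosing window stays as written.
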